### **8.4.4 Nontarget lesions**

When assessing nontarget lesions, the definitions in Table 6 apply.

## **9. DATA REPORTING AND REGULATORY REQUIREMENTS**

### **Multicenter Guidelines**

#### *The Protocol Chair*

The Protocol Chair, [name] is responsible for performing the following tasks:

- Coordinating, developing, submitting, and obtaining approval for the protocol as well as its subsequent amendments
- Assuring that all participating institutions are using the correct version of the protocol
- Taking responsibility for the overall conduct of the study at all participating institutions and for monitoring the progress of the study
- Reviewing and ensuring reporting of Serious Adverse Events (SAEs)
- Reviewing data from all sites

#### *Lead Center*

The Lead Center (Johns Hopkins) is responsible for performing the following tasks:

- Ensuring that IRB approval has been obtained at each participating site prior to the first patient registration at that site, and maintaining copies of IRB approvals from each site.
- Managing central patient registration
- Collecting and compiling data from each site
- Establishing procedures for documentation, reporting and submitting of AE's and SAE's to the Protocol Chair and all other applicable parties.
- Facilitating audits by securing selected source documents and research records from participating sites for audit, or by auditing at participating sites.

### *Participating PCCTC Sites*

Participating sites are responsible for performing the following tasks:

- Following the protocol as written, and the guidelines of Good Clinical Practice (GCP).
- Submitting data to the Lead Center
- Registering all patients with the Lead Center by submitting patient registration form, and signed informed consent promptly
- Providing sufficient experienced clinical and administrative staff and adequate facilities and equipment to conduct a collaborative trial according to the protocol
- Maintaining regulatory binders on site and providing copies of all required documents to the Lead Center
- Collecting and submitting data according to the schedule specified by the protocol

## **9.1 Data Entry**

Data collected during this study will be entered into a secure database. Staff at Johns Hopkins will be responsible for the initial study configuration and setup in the CRMS database and for any future changes.

### *9.1.1 Case report forms completion*

Case report forms will be generated by the coordinating center for the collection of all study data. Investigators will be responsible for ensuring that the CRFs are kept up-to-date.

The paper Eligibility Checklist CRF must be completed using black ink. Any errors must be crossed out so that the original entry is still visible, the correction clearly indicated and then initialed and dated by the individual making the correction.

eCRFs will be completed within 2 weeks of the patient coming to the clinic and all relevant supporting documentation such as scans, progress notes, nursing notes, blood work, pathology reports, etc., will be submitted via email to the Study Manager for remote monitoring approximately every 4-6 weeks when requested. All patient names or other identifying information will be removed prior to being sent to the Coordinating Center (SKCCC) or non- redacted source documents can be sent via a password -protected/ secured document transfer based on each institution's guidelines.

Authorized representatives of the Coordinating Center (SKCCC) may visit the satellite sites to perform audits or inspections, including source data verification. The purpose of these audits or inspections is to systematically and independently examine all trial-related activities and documents to determine whether these activities were conducted and data were recorded, analyzed, and accurately reported according to the protocol, Good Clinical Practice (GCP), and any applicable regulatory requirements.

**9.1.2 *Source documents***

Study personnel will record clinical data in each patient's source documents (i.e., the patient's medical record). Source documentation will be made available to support the patient research record. Study monitors will review entries on the CRFs at regular intervals, comparing the content with source documents.

**9.1.3 *Record retention***

The investigator will maintain adequate and accurate records to enable the conduct of the study to be fully documented and the study data to be subsequently verified. After study closure, the investigator will maintain all source documents, study-related documents, and the CRFs. Because the length of time required for retaining records depends upon a number of regulatory and legal factors, documents should be stored until the investigator is notified that the documents may be destroyed. In this study, records are to be retained and securely stored for a minimum of 5 years after the completion of all study activities.

**9.2 Data Management**

**9.2.1 *Lead research program coordinators***

A Lead research program coordinator at the coordinating center will be assigned to the study. A Lead Research Program Coordinator will manage the study activities at each of the participating sites. The responsibilities of the Lead Research Program Coordinator include project compliance, data collection, data entry, data reporting, regulatory monitoring, problem resolution and prioritization, and coordination of the activities of the protocol team.

**9.3 Clinical Trial Agreement**

This trial is being conducted under one or more clinical trial agreements that contain, among other terms, the publication policy, indemnity agreements, and financial arrangements for the study.

**9.4 Study Monitoring**

Study calls between sites will be held every 3 months to discuss accrual goals and AE/toxicity data. Interim analysis will be performed as described in Section 10.

**10. STATISTICAL CONSIDERATIONS**

The primary endpoint will be the proportion of subjects who achieve a PSA response, defined as a 50% or greater decline in PSA from baseline, confirmed on a subsequent

measurement at least 3 weeks apart. The treatment regimen would be considered of insufficient activity for further study in this population if the PSA response rate is 50% or less. The sample size is calculated to detect an improved PSA response rate from 50% to 75%. An optimal Simon two stage design is planned. A total of 12 patients will be entered in the first stage with a planned analysis for futility performed 12 weeks after the last patient began rucaparib. The number of patients allowed with a non-BRCA1, -BRCA2, or -ATM mutation in stage 1 will be capped at 3. If 6 or fewer subjects have a PSA response, the study will be terminated and we will conclude the regimen is ineffective. If  $\geq 7$  subjects respond, then an additional 16 patients will be studied, for a total of 28 patients. If a total of 17 or fewer subjects respond in stage one and two combined, we consider this regimen ineffective. If a total of 18 or more respond, we conclude the regimen is promising and warrants further study. The maximum sample size will be increased to 30 patients to account for possible dropouts. The total number of patients (stage 1 and 2) allowed with a non-BRCA1/ -BRCA2 mutation will be capped at 10; this will ensure that at least 20 men will be enrolled with germline BRCA1/BRCA2 mutations.

This design provides 90% power to detect an absolute 25% increase in PSA response rate with a one-sided type I error of 0.1. The probability of early stopping is 0.61 under the null hypothesis that the PSA Response Rate is 50%.

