Objectives	Primary

To estimate the PSA50 response rate to rucaparib in patients with metastatic and non-metastatic prostate cancer that harbor an inactivating mutation in a homologous recombination DNA repair gene while on treatment with rucaparib, defined as a decline in PSA to 50% of baseline level, confirmed with a second measurement at least 4 weeks apart (PCWG3).

Secondary

- To estimate the median PSA progression-free survival (PCWG3).
- To estimate the median progression-free survival (PCWG3).
- To estimate the objective response rate (ORR) in those patients with measurable disease.
- To determine the safety/tolerability of rucaparib in a population of men with hormone sensitive prostate cancer.

Correlatives/Tertiary

- To measure the quantitative change in gamma-H2AX, RAD51, 53BP1 formation in tumor tissue following treatment with rucaparib (M1 disease only).
- To develop an RNA expression signature associated with response to rucaparib (M1 disease only).
- To estimate the percentage of patients with a loss-of-function mutation or total allelic loss of second somatic gene allele (i.e. LOH, or biallelic inactivation) (In all patients undergoing biopsy or with archived tissue).
- To investigate any association between PARP-1 and PARP-2 protein and mRNA expression levels in tumor with response to rucaparib (In all patients undergoing biopsy or with archived tissue).
- To examine the incidence of reversion mutations in circulating tumor DNA at clinical progression.

[figure not shown]

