**Study design**

The study is an open-label single arm Phase II trial. Eligible patients are those with metastatic hormone-sensitive prostate cancer (mHSPC) or high-risk biochemically recurrent prostate cancer (BCR). All patients must have a documented germline or somatic mutation in a homologous recombination DNA-repair gene (BRCA1, BRCA2, ATM, CHEK2, NBN, BRIP1, RAD50, RAD51C, RAD51D, PALB2, MRE11, FANCA, FANCB, FANCC, FANCD2, FANCE, FANCF, FANCG, FANCI, FANCL, FANCM). Germline genetic testing and molecular sequencing as a screening for eligibility will not be offered. A mandatory tumor biopsy will be performed prior to the start of therapy in all patients with metastatic disease (if tumor material is not successfully obtained at the time of biopsy, then archival material will be sought). A second, OPTIONAL tumor biopsy will take place after three months of therapy.

After enrollment, patients will be treated with rucaparib at the established dose of **600mg by mouth twice daily**. Patients will be followed monthly with clinic visits, safety labs (including CBC w/diff, Comp), PSA, and toxicity assessments. Treatment [with a minimum drug exposure of 12 weeks] will be continued until PSA progression (PCGW3 criteria) or clinical/radiographic progression (whichever comes first), or until unmanageable toxicity requiring drug cessation. Patients who remain on treatment

for >12 months can begin to have their clinic visits, safety labs (including CBC w/diff, Comp), PSA, and toxicity assessments every 3 months.

A trial schema for study treatment appears below:

Criteria for evaluation

Primary Endpoint

- PSA50 response rate, defined as a decline in PSA to  $\geq 50\%$  of baseline level, confirmed with a second measurement at least 4 weeks later (PCWG3).

Secondary Endpoints

- Safety/Tolerability, defined as incidence of CTCAE v5.0 grade  $\geq 3$  toxicities experienced by patients on the trial.
- PSA progression-free survival, defined as a time from initiation on rucaparib therapy until PSA increase of 25%, confirmed with another measurement at least 4 weeks later (PCWG3).
- Radiographic progression-free survival (PCWG3): time to radiographic or clinical progression or death, whichever comes first. Based on RECIST version

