## 5.2 Treatment/Intervention Period (Day 1 of each 28 day cycle +/- 3 days, ongoing)

Patients will be seen on D1 of each cycle of rucaparib (consisting of 28 days, +/- 3 days). The following assessments will be performed at each visit:

- conduct physical exam (including vital signs, weight)
- obtain any medical history changes from prior assessment
- assess performance status (ECOG). (Appendix A)
- review concurrent medications (see Appendix B for a listing of medications with the potential for drug interactions)
- Patients who remain on treatment for >12 months can begin to have their clinic visits, safety labs (including CBC w/diff, Comp), PSA, and toxicity assessments every 3 months.

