#### 8.1.1 Primary endpoint

The primary endpoint is defined as a PSA50 response, defined as a decline in PSA to ≥50% of baseline level, confirmed with a second measurement at least 4 weeks later.

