## 10.1 Study Endpoints

### 10.1.1 Analysis of the primary endpoint

The primary endpoint of this study is PSA50 response, defined as a decrease in the PSA to 50% less than the baseline PSA upon enrollment in the trial. The decrease must be confirmed by a second measurement at least 4 weeks apart. For purposes of meeting the primary endpoint, patients will be considered to have done so if they have a PSA50 response only while on therapy with rucaparib. PSA values will be measured each cycle during the trial. All patients who are administered at least one dose of rucaparib will be considered evaluable for the primary endpoint. If patients do not have follow-up PSAs after initiation rucaparib therapy due to stopping therapy for toxicity or withdrawing consent, for example, then they will be replaced.

We will estimate the PSA50 response rate, along with the exact 95% confidence interval, for the population of patients.

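### The primary endpoint has two confirmation intervals (3 and 4 weeks), and the 12-week futility stop counts a 50% PSA decline still awaiting confirmation as non-response

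*Combined protocol and SAP*

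**What the plan says.** **Confirmation interval.** The opening of Section 10, which also sets the decision rules, asks for a confirming "measurement at least 3 weeks apart". Section 10.1.1, the analysis of the primary endpoint, says: "The decrease must be confirmed by a second measurement at least 4 weeks apart". Section 8.1.1 says "confirmed with a second measurement at least 4 weeks later". The synopsis gives 4 weeks three times: under the objectives, the criteria for evaluation and the statistical method. Of six statements of the primary endpoint, five say 4 weeks and one says 3.

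**Size of the decline.** Section 10 requires a fall of at least 50% from baseline. Section 8.1.1 has the response "defined as a decline in PSA to ≥50% of baseline level", and the synopsis criteria for evaluation use the same wording.

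**Schedule.** PSA is measured once per 28-day cycle, with a visit window of 3 days either side (Sections 5.2 and 10.1.1). A response counts only while the patient is on rucaparib (Section 10.1.1).

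**Futility look.** Twelve patients enter stage 1, "with a planned analysis for futility performed 12 weeks after the last patient began rucaparib". The study stops at 6 or fewer responders. Otherwise 16 more patients enter, and 18 or more responders of 28 is a promising result. Section 10 states 90% power at a 75% rate, a one-sided type I error of 0.1, and a 0.61 probability of early stopping at a 50% rate.

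**The concern.** The two intervals are both in current text, a few lines apart, and the visit window allows gaps that satisfy one and fail the other. Both decision rules turn on a single patient (6 against 7 of 12, 17 against 18 of 28), so one ambiguous status can decide the trial.

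The wording about a decline to at least 50% of baseline adds a second ambiguity. Read literally, it admits a PSA that has fallen only to 60% of baseline.

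The futility look raises a different problem. A response may first appear at any time on rucaparib, but the look is tied to a calendar point. The last entrant has PSA values at about weeks 4, 8 and 12, so a first decline at week 12 cannot be confirmed until about week 16. An earlier entrant whose first decline came at his most recent visit is also pending. Such men count as non-responders for a mandatory stop, yet may be responders in the final count. The stated power and early-stopping probability assume that a patient's status is the same at both times.

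**Working it through.** **1. The plan's own figures.** Let X1 ~ Bin(12, p) and X2 ~ Bin(16, p), with complete stage-1 status.
- Early stopping, P(X1 ≤ 6): 0.613 at p = 0.50 (stated 0.61) and 0.054 at p = 0.75.
- Success, P(X1 ≥ 7 and X1 + X2 ≥ 18): 0.0815 at p = 0.50 (limit 0.1) and 0.9017 at p = 0.75 (stated 90%).

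The design reproduces.

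**2. When the interval matters.** Each visit may move by up to 3 days, so consecutive draws are 28 ± 6 = 22 to 34 days apart. Of the 7 × 7 = 49 pairs of visit days, 21 give a gap under 28 days and none a gap under 21. This counts possibilities and does not forecast frequency. Draws two cycles apart are 56 ± 6 = 50 to 62 days apart and confirm under either rule. Status therefore differs only when the sole confirming draw on rucaparib falls at 22 to 27 days.

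**3. Effect of one reclassified responder.** Suppose exactly one responder under the 3-week rule is lost under the 4-week rule.
- Stage-1 patient: P(X1 ≥ 7, X1 + X2 ≥ 18) − P(X1 ≥ 8, X1 + X2 ≥ 19). At p = 0.75 this is 0.9017 − 0.7778 = 0.124. At p = 0.50 it is 0.0815 − 0.0333 = 0.048.
- Stage-2 patient: P(X1 ≥ 7, X1 + X2 = 18) = 0.059 at p = 0.75 and 0.041 at p = 0.50.

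These are conditional on such a patient existing.

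**4. Pending declines at the look.** Time to response is not in the documents, so the following inputs are assumptions. Let k stage-1 patients be affected, and let each eventual responder among them have chance f of being confirmed by the look. Let U ~ Bin(12 − k, p) be the responders among the others, A ~ Bin(k, p) the eventual responders among the affected, and C ~ Bin(A, f) those confirmed in time. The trial continues if U + C ≥ 7 and succeeds if U + A + X2 ≥ 18. The last two rows instead leave each eventual responder among all 12 pending with probability 5% or 10%.

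| Assumption | Power (75%) | Wrong stop (75%) | Early stop (50%) | Type I error |
|---|---|---|---|---|
| Complete status | 90.2% | 5.4% | 0.61 | 8.1% |
| k = 1, f = 90% | 89.7% | 6.0% | 0.62 | 8.0% |
| k = 1, f = 70% | 88.7% | 7.2% | 0.65 | 7.8% |
| k = 1, f = 50% | 87.7% | 8.5% | 0.67 | 7.6% |
| k = 2, f = 90% | 89.1% | 6.7% | 0.64 | 7.9% |
| k = 2, f = 70% | 86.8% | 9.5% | 0.68 | 7.4% |
| k = 2, f = 50% | 84.1% | 12.7% | 0.72 | 6.8% |
| 5% pending, all 12 | 86.4% | 9.9% | 0.68 | 7.4% |
| 10% pending, all 12 | 80.8% | 16.1% | 0.74 | 6.4% |

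Check of one row by hand: for k = 1 and f = 50%, wrong stopping is 0.0544 + 0.75 × P(Bin(11, 0.75) = 6) × (1 − 0.5) = 0.0544 + 0.75 × 0.0803 × 0.5 = 0.0845.

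**5. Bound for a waiting rule.** A futility stop can only remove trials that would otherwise succeed. With no stop at all, type I error is P(Bin(28, 0.5) ≥ 18) = 0.0925, below 0.1.

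**The case against.** On the interval, five of six statements agree, including the dedicated analysis section, and PSA is drawn every cycle. A decline that persists on treatment is confirmed under either rule by a later draw. The exposed patient must leave rucaparib soon after a confirming draw at 22 to 27 days. That stands: the case is probably uncommon, and the percentages in step 3 are not estimates of risk to this trial. The conflict still sits in the paragraph that carries the decision rules.

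On the look, Section 10 defines response as confirmed and then applies the stop to that defined term, so the text is not silent. This also stands. A reader might infer that pending declines could be counted as responses, which would weaken the stop, but that contradicts Section 10's own definition. Section 10.2.1 treats unknown status as treatment failure; it concerns response categories in the main analysis and does not mention the look. What remains is that the literal rule can stop the trial on a status the final analysis would reverse.

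The sizes in step 4 depend on assumed timing. A reader might take the one- and two-patient rows as a ceiling, on the ground that only the latest entrants can be pending. The documents do not support that, because any stage-1 patient whose first decline came at his latest visit is pending, whenever he enrolled. The rows are illustrations, not bounds.

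**Conclusion.** The interval is wrong as written. The primary endpoint has two incompatible confirmation rules in current text, and Section 8.1.1 and the synopsis also misstate the size of the decline. The practical effect is probably small and its frequency cannot be derived from the documents. If exactly one responder is reclassified, the conclusion changes in 12.4% (stage 1) or 5.9% (stage 2) of trials at a 75% rate, and in 4.8% or 4.1% at 50%.

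For the futility look the plan can be applied as written, but a better rule is available at little cost. Under the illustrated assumptions power lies between 89.7% and 80.8%, and wrong stopping at a 75% rate between 6.0% and 16.1% against 5.4%. The true size depends on time to response.

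A reader might infer that the sample size is wrong or that a positive result would be unsafe. Neither follows: the design figures reproduce, and counting pending declines as non-response lowers type I error.

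**What to change.** 1. Use one endpoint definition everywhere: a fall in PSA of 50% or more from baseline, with one confirmation interval. Four weeks is what five of the six statements say. If it is kept, state that a consecutive cycle visit within its window satisfies it. This changes wording only; the design figures stand.
2. At the look, do not apply the stop while confirmed responders plus patients on rucaparib with an unconfirmed 50% decline total 7 or more. Wait for the confirmatory PSA, then apply the 6-of-12 rule. Type I error cannot exceed 9.2%.
3. State that the 90% power and the 0.61 early-stopping probability assume complete stage-1 status. The waiting rule does not recover men whose first decline comes after the look.

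The cost is a delay of about 4 weeks when the wait is triggered. With exactly k pending patients and the other 12 − k responding at rate p, that probability is P(7 − k ≤ Bin(12 − k, p) ≤ 6). For k = 1 it is 22.6% at a 50% rate and 8.0% at 75%; for k = 2 it is 45.1% and 20.4%. If enrolment continued during the wait, the planned 30 patients in 24 months (1.25 a month) would add about one patient. The maximum sample size does not change.

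### The final cut-off of 18 responders is derived for 28 patients, but 30 are planned and no cut-off is given for 29 or 30, so the stated one-sided type I error of 0.10 is not guaranteed

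*Combined protocol and SAP*

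**What the plan says.** Section 10 continues past stage 1 if at least 7 of the first 12 men respond; "then an additional 16 patients will be studied, for a total of 28 patients". The final rule follows: "If a total of 17 or fewer subjects respond in stage one and two combined, we consider this regimen ineffective", and "If a total of 18 or more respond, we conclude the regimen is promising and warrants further study". The next sentence reads "The maximum sample size will be increased to 30 patients to account for possible dropouts". The sample size part of the synopsis repeats all of this. The stated properties are 90% power for 75% against 50%, a one-sided type I error of 0.1, and a 0.61 probability of early stopping under the null.

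Other places bear on how many men are counted:

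- Section 3.2 and the synopsis (expected enrollment) plan 30 patients.
- Section 10 caps one mutation group: "The total number of patients (stage 1 and 2) allowed with a non-BRCA1/ -BRCA2 mutation will be capped at 10", and adds that "this will ensure that at least 20 men will be enrolled with germline BRCA1/BRCA2 mutations".
- Section 10.1.1: "All patients who are administered at least one dose of rucaparib will be considered evaluable for the primary endpoint". Section 10.2.1 puts all eligible men with at least one dose in the main response analysis.
- Section 10.1.1 also says of men with no follow-up PSA, "due to stopping therapy for toxicity or withdrawing consent, for example, then they will be replaced". The synopsis has the same rule.

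**The concern.** The cut-off of 18 belongs to 12 + 16 = 28 patients. A fixed number of responders becomes easier to reach as more men are counted, so the same 18 is a weaker test at 29 or 30. The plan gives no cut-off for those numbers and does not say that only 28 men enter the decision.

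The replacement sentence does not settle it, because it does not say whether a replaced man stays in the denominator. Next to the rule that one dose makes a man evaluable, two readings are possible:

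- (a) 29 or 30 men with a real chance of response are counted.
- (b) Places 29 and 30 only stand in for men who never had a follow-up PSA.

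This rule decides whether the regimen is called promising. The outcome in dispute is exactly 18 responders. If the denominator is settled after responses are known, the verdict at 18 is open to choice.

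**Working it through.** **Inputs** (Section 10): null rate 0.50, target rate 0.75, stage 1 size 12, continue with 7 or more, final size n = 28, success with 18 or more, enlarged maximum 30. The documents give no dropout rate.

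**Formula.** With X1 ~ Bin(12, p) and X2 ~ Bin(n − 12, p), independent, and final cut-off c:

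P(success) = Σ over x = 7 to 12 of P(X1 = x) × P(X2 ≥ c − x).

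Alpha is this sum at p = 0.50 and power is the sum at p = 0.75.

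**Step 1. The plan's own design (n = 28, c = 18), with n = 30 alongside, at p = 0.50:**

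| x | P(X1 = x) | P(X2 ≥ 18 − x), n = 28 | product | P(X2 ≥ 18 − x), n = 30 | product |
|---|---|---|---|---|---|
| 7 | 0.19336 | 0.10506 | 0.02031 | 0.24034 | 0.04647 |
| 8 | 0.12085 | 0.22725 | 0.02746 | 0.40726 | 0.04922 |
| 9 | 0.05371 | 0.40181 | 0.02158 | 0.59274 | 0.03184 |
| 10 | 0.01611 | 0.59819 | 0.00964 | 0.75966 | 0.01224 |
| 11 | 0.00293 | 0.77275 | 0.00226 | 0.88106 | 0.00258 |
| 12 | 0.00024 | 0.89494 | 0.00022 | 0.95187 | 0.00023 |
| Sum | | | **0.0815** | | **0.1426** |

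At 28, power is 0.9017 and P(X1 ≤ 6) at p = 0.50 is 0.6128. All three figures agree with the plan. A search over two-stage designs with alpha ≤ 0.10 and power ≥ 0.90 also returns 6/12 and 17/28 as the optimal design.

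**Step 2. Other numbers counted, stage 1 unchanged:**

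| Number counted | Cut-off | Alpha | Power |
|---|---|---|---|
| 28 | 18 | 0.081 | 0.902 |
| 29 | 18 | 0.111 | 0.923 |
| 30 | 18 | 0.143 | 0.934 |
| 29 | 19 | 0.061 | 0.887 |
| 30 | 19 | 0.086 | 0.914 |

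At 29, no cut-off meets both stated targets: 18 breaks alpha and 19 leaves power at 88.7%.

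**Step 3. The disputed outcome.** Probability of passing stage 1 and ending with exactly 18 responders:

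| Number counted | p = 0.50 | p = 0.75 |
|---|---|---|
| 28 | 0.041 | 0.059 |
| 29 | 0.050 | 0.036 |
| 30 | 0.057 | 0.020 |

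At 28, this result favours the target rate. At 29 and 30, it is likelier under the null. The exact 95% interval for 18 of 30 is 0.406 to 0.773.

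**Step 4. Reading (b).** Enrol until 28 men are assessed or 30 are treated, read stage 1 at the 12th assessed man, take 50% or 75% as the rate among assessed men, and keep the cut-off of 18. Without dropout, alpha is 0.081. The dropout rates below are assumptions.

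| Assumed dropout | Alpha | Power |
|---|---|---|
| 3.3% (1/30) | 0.079 | 0.898 |
| 6.7% (2/30) | 0.070 | 0.876 |
| 10% | 0.056 | 0.831 |

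**Step 5. Where the planned enrolment points.** The promised 20 men with the named mutations follow from 30 − 10 = 20. With 28 it would be 28 − 10 = 18. The cap therefore assumes that 30 men are enrolled over stages 1 and 2.

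**The case against.** The strongest reply is that the text describes a ceiling that protects 28. The test is completed at 28, the maximum is raised for dropouts, and men without a follow-up PSA are replaced. On that reading alpha is at most 0.081.

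There is also a middle case. Suppose all 30 are counted, dropouts stay in as non-responders, and the null is 50% among assessed men. With the cut-off of 18, alpha is then 0.107, 0.078 and 0.055 at assumed dropout of 3.3%, 6.7% and 10%. If dropout matches the allowance of 2 in 30, the unchanged rule holds. The figures 0.111 and 0.143 therefore need essentially no dropout among the men counted.

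Further, the primary objective is estimation, with an exact interval planned; only one outcome is in dispute; and the mutation cap concerns men enrolled, not the denominator of the test.

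Much of this stands as a limit on size. It makes the excess conditional, and the cap shows only that 30 are to be enrolled. It does not close the gap. Section 3.2 plans to include 30, Section 10.1.1 makes every treated man evaluable, Section 10.2.1 counts every eligible treated man, and nothing restricts the test to 28. With few dropouts, the rule as written exceeds its stated error. The interval would show weak evidence at 18 of 30 but would not say which conclusion the decision rule gives.

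**Conclusion.** The concern holds. The 28-patient design is correct, but the plan does not define the decision for the number it intends to enrol. Alpha is 0.111 at 29 and 0.143 at 30 if all men counted have the null 50% chance of response and stage 1 stays at 7 of 12. It is at most 0.081 if the extra places only replace men without a follow-up PSA and 50% is the null rate among assessed men. The documents allow either reading and give no dropout rate, so the stated 0.10 is not guaranteed; they do not show that it is exceeded. This should be fixed before responses are known.

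**What to change.** **Preferred.** In the synopsis and Section 10, keep 7 or more of 12 at stage 1 and state the final cut-off by the number counted in the primary analysis: 18 or more of 28, 19 or more of 29, 19 or more of 30. Even if the final number were chosen among these after seeing responses, alpha would be at most 0.096. If fewer than 28 are counted, keeping 18 is conservative (alpha 0.056 at 27, power 0.865); a sentence should say so.

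In the synopsis and Section 10.1.1, reconcile the one-dose rule with the replacement sentence and align both with Section 10.2.1. State whether a replaced man stays in the denominator at each stage, and when accrual ends (for example at 28 men with a follow-up PSA or 30 treated, whichever comes first). The replacement rule need not be deleted.

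**Acceptable alternative.** Confine the test to the first 28 evaluable men, define evaluable as having a follow-up PSA, state that 50% and 75% are rates among these men, and keep the cut-off of 18.

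**Cost.** No extra patients. Under the preferred form, one more response is needed at 29 or 30, and the stated 90% power must be qualified because it is 88.7% at 29. If 75% applies only to assessed men, power depends on the choice (dropout rates are assumptions):

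| Rule | 3.3% | 6.7% | 10% |
|---|---|---|---|
| First 28 evaluable, at most 30 treated, cut-off 18 | 0.898 | 0.876 | 0.831 |
| Replaced men kept in the final denominator, cut-off by number treated, stage 1 read at the 12th assessed man | 0.858 | 0.809 | 0.737 |
| 30 treated, dropouts as failures, no replacement, cut-off 19 | 0.860 | 0.787 | 0.698 |

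The alternative loses the least power, but it leaves replaced men out of the test, so the one-dose rule must then be reworded.
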